8.3.2. Exposure

- The main exposure variable is Treatment with eltrombopag, including dose, duration of treatment, drug discontinuation, In combination with peginterferon, ribavirin, and direct acting antiviral agents (triple therapy)

8.3.3. Other Covariates

Demographics: Age, Sex, Race/ethnicity

Co-morbidities: Diabetes mellitus, cardiovascular or cardiac disease/conditions, lipid disorders, neurological disorders, pulmonary diseases/conditions, substances that contribute to co-morbid conditions (current or historical smoking, alcohol and substance abuse), coagulation disorders, prior/current malignancies including hepatocellular carcinoma, chronic skin disease, including dermatologic extrahepatic manifestation of CHC, HIV or HBV coinfection, other forms of liver disease (i.e. hemochromatosis, NASH), pre-existing complications of liver disease if present or being treated at baseline (ascites, encephalopathy, esophageal varices).

Virology data

History of Cirrhosis: liver biopsy results and/or clinical/histological diagnosis of cirrhosis

Concomitant Medications

8.4. Data sources

In HCV-TARGET, patients are enrolled prospectively at participating sites and treated per local standard of care. HCV-TARGET does not define treatment regimens, dosing, or duration or safety management practices. Source data is the original medical record. All original clinic notes, telephone notes, safety and efficacy labs collected during treatment observation period are submitted to a central data repository. Patient data from submitted records is abstracted at the HCV-TARGET clinical coordinating centre. Where possible, data can be mapped directly from electronic medical records for transfer into the registry database. These data include:

- Baseline factors (HCV viral load, HCV genotype, cirrhosis determination, prior HCV treatment, medical history, co-morbid conditions, IL-28b genotypes)
- HCV treatment regimen and dose adjustments
- Adverse events associated with anti-HCV therapy
- Concomitant medications (baseline and on treatment)
- Long-term post treatment follow-up (co-morbid conditions, complications related to liver disease, and mortality)

The eltrombopag cohort study nested within HCV-TARGET will include all pertinent data from HCV-TARGET.

8.5. Study size

It is estimated that between 1-3% of the 5000 HCV-TARGET patients will receive eltrombopag and be eligible for the nested eltrombopag cohort study, for a sample size between 50 and 150 patients. Almost all of these patients will be taking direct acting antivirals. As of January 2014, approximately 2700 patients have been enrolled into HCV-TARGET; 2.1% of patients have used eltrombopag.

Since this is a descriptive study, sample size informs the degree of precision around point estimates for the events of hepatic decompensation and thromboembolic events.

The event rate of hepatic decompensation in this specific population is unknown. The rate that occurred among eltrombopag users in the combined ENABLE trials, which was 10% (Afdhal, 2014), is used as an estimate, and for sample size calculation this rate is varied from 8% to 12%.

Figure 1 below depicts the precision around potential event rates. Number of assumed eltrombopag users is marked by different colored lines and symbols. The x-axis notes the percentage of patients with an event. The y-axis is the precision for each specific event rate, which can be added and subtracted to the point estimate to obtain a 95% confidence interval. For example, if 10% of patients experience a hepatic decompensation event, the half width varies across sample size as follows:

Sample Size	Half Width
50	0.083
100	0.058
150	0.047
200	0.041

A similar figure is presented for the event rate for thromboembolic events, using the ENABLE trials event rate of 3% (Afdhal, 2014) as the mid-point and varying the rate from 1% to 5% (Figure 2).

Figure 1 Precision (y-axis) for event rates (x-axis) ranging from 8%-12% for the outcome of hepatic decompensation for 4 potential sample sizes of eltrombopag users (different colored lines)

[figure not shown]
[figure not shown]

Figure 2 Precision (y-axis) for event rates (x-axis) ranging from 1%-5% for the outcome of thromboembolic events for 4 potential sample sizes of eltrombopag users

Calculations and graphs have been derived using the NPASS software [Hintze, 2006]

The study is not designed to compare hepatic decompensation rates in eltrombopag users with rates in a control group of HCV-TARGET patients not using eltrombopag due to insufficiency of the sample size to draw statistical inferences. Based on the enrolment

rate of 2.1%, it is estimated that 105 eltrombopag patients will comprise the nested HCV-TARGET cohort study when all 5000 HCV-TARGET patients have been enrolled.

For hepatic decompensation, the power to detect a doubling in event rates comparing users to non-users in HCV-TARGET, assuming the ENABLE clinical trial rate of 10% in the eltrombopag treated group and 5% in placebo patients is:

- 19% if there is propensity-score matching of eltrombopag users to non-users on a 1:1 basis
- 30% if matched 1:2
- 36% if matched 1:3
- 39% if matched 1:4
- 42% if matched 1:5
- 44% if matched 1:6.

This assumes that 5 patients of the 105 projected users can not be propensity-scored matched, which is conservative given that eltrombopag users compared to non-users could differ on important factors in addition to eltrombopag use, such as presence of thrombocytopenia, level of thrombocytopenia, MELD score, serum albumin, and site (representing physician preference or medical care standard).

Additionally, the study is not powered to detect a difference in hepatic decompensation or in mortality comparing patients who achieve SVR to patients who do not achieve SVR. A separate research study is being conducted by GSK to address this question and it will enrol 200 patients (with approximately 150 patients needed for adequate power and 50 additional patients to be included to allow for potential overly liberal rate assumptions and for drop outs).

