8.7. Data analysis

The eltrombopag cohort study nested within HCV-TARGET is a descriptive study conducted to provide primarily incidence of hepatic decompensation and secondarily other important outcomes such as thromboembolic events and mortality in HCV patients who are treated with direct acting anti-viral agents as part of their interferon-based regimen, a group of patients not previously studied in the randomized clinical trials. Cumulative incidence rates will be calculated for the occurrence of hepatic decompensation, thromboembolic events, or mortality, as separate events, at multiple time points during the study and at the end of the 3-year follow-up period. The 95% CIs for cumulative incidence will be calculated using the method outlined by Newcombe et al [Newcombe, 1998]. Baseline factors potentially related to each event will be identified during exploratory analyses by comparing Kaplan-Meier survival estimates for patients with vs. without the factor and testing for statistical significance using the log-rank test. Cox proportional hazards models will be constructed to evaluate the influence of these identified factors simultaneously.

Kaplan-Meier survival estimates will be calculated for the outcomes of hepatic decompensation, thromboembolic events, and all-cause mortality. Thromboembolic events will be presented as a single category as well as grouped by venous or arterial origin, and by individual event types. Confidence intervals for survival rates will be calculated using the method outlined by Simon et al [Simon, 1986]

Patient demographics and characteristics will be described at the time of initiation of eltrombopag. Virology, laboratory information, information on dose and duration of eltrombopag, early and sustained virologic response, anti-viral therapy and incidence of hepatic decompensation and thromboembolic events will be described at baseline and distinct follow-up time points. Continuous variables will be reported as mean, standard deviation, median, 25th and 75th quartiles, and range. Categorical variables will be summarized as number and proportion of subjects with observed (non-missing) data, with corresponding 95% confidence intervals (CI) by exact methods.

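### The symmetric half-widths in section 8.5 put the upper 95% limit on harm lower than score or exact intervals of the kind section 8.7 plans

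*Protocol*

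**What the plan says.** Section 8.5 of the protocol calls the study descriptive and uses sample size to show how precisely event rates will be estimated. It expects 1% to 3% of the 5000 registry patients to use eltrombopag, "for a sample size between 50 and 150 patients". From the 2.1% observed so far it projects a single number: "it is estimated that 105 eltrombopag patients will comprise the nested" cohort.

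Precision is given as one number per rate and sample size, "which can be added and subtracted to the point estimate to obtain a 95% confidence interval". The worked example reads "if 10% of patients experience a hepatic decompensation event, the half width varies across sample size as follows": 0.083 for n = 50, 0.058 for 100, 0.047 for 150 and 0.041 for 200. Figure 1 covers decompensation rates of 8% to 12%. Figure 2, described as similar, covers thromboembolic rates of 1% to 5% around a mid-point of 3%. Neither figure is reproduced in the text at hand. The formula behind the table is not named, and no finite-population correction is mentioned.

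Section 8.7 states: "The 95% CIs for cumulative incidence will be calculated using the method outlined by" a cited paper. The reference list shows that this paper compares seven two-sided intervals for a single proportion, and the protocol does not say which of them is meant. Section 8.7 also plans exact 95% intervals for categorical variables.

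**The concern.** At low event rates and with 50 to 150 patients, score and exact intervals for a proportion are asymmetric: the upper arm is longer than the lower. One half-width applied in both directions cannot reproduce them. For a harm, the upper limit matters most, and that is the limit the symmetric rule makes too favourable. For rare events the rule can also give a lower limit below zero.

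The study is a post-authorisation safety study requested by the EMA (section 11.1). Section 8.5 disclaims power for comparative questions, so the precision statement is what tells a regulator how informative the cohort will be. If the report uses a different kind of interval, its upper limits will be higher than the protocol led the reader to expect.

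**Working it through.** **Inputs.** From section 8.5: 95% two-sided confidence (z = 1.96); decompensation rate p = 0.10; thromboembolic rate p = 0.03; n = 50, 100, 150, 200 from the table and 105 as projected; registry size N = 5000. Assumed: the Wilson score interval stands in for the unnamed method of section 8.7. The exact (Clopper-Pearson) interval is shown beside it.

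**Step 1: reproduce the stated half-widths (p = 0.10).**

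Plain Wald: h = 1.96 × √(p(1 − p)/n). For n = 100, 1.96 × √(0.09/100) = 0.0588.

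With a finite-population correction: h × √((N − n)/(N − 1)). For n = 100, 0.0588 × √(4900/4999) = 0.0582.

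| n | Stated | Plain Wald | Wald, corrected for N = 5000 |
|---|---|---|---|
| 50 | 0.083 | 0.0832 | 0.0828 |
| 100 | 0.058 | 0.0588 | 0.0582 |
| 150 | 0.047 | 0.0480 | 0.0473 |
| 200 | 0.041 | 0.0416 | 0.0407 |

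The corrected column rounds to all four stated values. Plain Wald rounds to 0.083, 0.059, 0.048 and 0.042. Wilson, exact, Agresti-Coull and continuity-corrected versions do not give all four. The correction is inferred from this match; its effect is below 0.001 in every row.

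**Step 2: limits at a 10% rate.**

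Wilson limits: [p + z²/(2n) ± z√(p(1 − p)/n + z²/(4n²))] / (1 + z²/n). For n = 100, the centre is (0.1 + 0.0192)/1.0384 = 0.1148 and the half-width is 1.96 × √(0.0009 + 0.000096)/1.0384 = 0.0596. The limits are 5.5% and 17.4%.

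| n | Stated rule | Wilson | Exact |
|---|---|---|---|
| 50 | 1.7% to 18.3% | 4.3% to 21.4% | 3.3% to 21.8% |
| 100 | 4.2% to 15.8% | 5.5% to 17.4% | 4.9% to 17.6% |
| 150 | 5.3% to 14.7% | 6.2% to 15.8% | 5.7% to 16.0% |
| 200 | 5.9% to 14.1% | 6.6% to 14.9% | 6.2% to 15.0% |

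The stated upper limit falls short of Wilson by 3.1, 1.6, 1.1 and 0.8 percentage points. Half the total Wilson width is 0.085, 0.060, 0.048 and 0.042, within about 0.002 of the stated values. The problem is therefore location: both ends are too low. At the projected n = 105, plain Wald gives 4.3% to 15.7% and Wilson 5.6% to 17.2%.

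**Step 3: limits at a 3% rate, if Figure 2 follows the same rule.**

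For n = 50, 1.96 × √(0.03 × 0.97/50) = 0.0473.

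| n | Wald | Wilson |
|---|---|---|
| 50 | −1.7% to 7.7% | 0.7% to 12.0% |
| 100 | −0.3% to 6.3% | 1.0% to 8.5% |
| 105 | −0.3% to 6.3% | 1.1% to 8.3% |
| 150 | 0.3% to 5.7% | 1.2% to 7.1% |
| 200 | 0.6% to 5.4% | 1.4% to 6.4% |

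The exact upper limit at n = 50 is 12.2%. Over rates of 1% to 5%, in steps of one point, the Wald lower limit is negative at all rates for n = 50, at 1% to 3% for n = 100 and 105, at 1% and 2% for n = 150, and at 1% for n = 200. The finite-population correction changes none of these signs. Some cells, such as 3% of 50, are not whole numbers of events; as planning values they serve the same purpose as the protocol's own.

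**The case against.** The best defence is that the table is illustrative and nothing depends on it. The cohort is every eltrombopag user in the registry, so its size is set by availability. There is no target width, threshold or test, and section 8.9 openly names the small sample as a major limitation. The table also reports half-widths, and as half-widths the values are nearly right. All of this stands, and it keeps the point minor. It does not rescue the instruction to add and subtract, which turns a nearly correct width into a misplaced interval.

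A second defence is that section 8.7 does not identify its method, so the size of the discrepancy rests on an assumption. That also stands. The text does not even rule out that the simple normal interval is the one intended. But section 8.7 separately plans exact intervals, and Wilson and exact limits agree closely, so the conclusion does not turn on which of those two is used.

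Three stronger readings are tempting, and the documents do not support them:

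- A reader comparing the table with plain Wald might infer that three of the four entries are miscalculated. All four reproduce once a correction for N = 5000 is applied, and the gap is about 0.001. The fair criticism is that the correction is undisclosed and hard to justify, because the cohort is all users (section 8.1) and not a random sample of the registry.
- A reader might infer that the protocol prints impossible thromboembolic limits. It prints none in its text, Figure 2 cannot be seen, and at 3% the lower limit is not negative for n = 150 or 200.
- A reader might infer that the study is too small for its purpose. Nothing here shows that.

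**Conclusion.** The point holds as a minor one. Section 8.5 presents a symmetric normal-approximation interval as the 95% interval, while section 8.7 points to single-proportion or exact methods. At a 10% decompensation rate this understates the upper limit by 0.8 to 3.1 percentage points against Wilson, most at n = 50, and by 0.9 to 3.5 points against exact. Total width is almost unchanged. At a 3% thromboembolic rate and n = 50, the upper limit would be 7.7% against about 12%, with a negative lower limit at n = 50, 100 and 105.

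The decompensation result assumes that the report will use a score or exact interval. The thromboembolic result assumes in addition that Figure 2 follows the rule stated for Figure 1. The finite-population correction is inferred and immaterial in size.

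**What to change.** Name in section 8.7 the one interval method to be used for cumulative incidence. In section 8.5, replace the half-width table and both figures with lower and upper 95% limits from that method, without a finite-population correction. Give them for n = 50, 105 and 150 at the rates already chosen (8% to 12% for decompensation, 1% to 5% for thromboembolic events). Delete the sentence that tells the reader to add and subtract the half-width.

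The cost is one recalculation of a table and two figures. The stated upper limits become less favourable; enrolment and conduct do not change.

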8.6. Data management

Data is transmitted to the Data Coordinating Center (DCC) at the University of North Carolina via a distributed web-based data entry system that is 21 CFR Part 11 validated and compliant. The DCC in conjunction with the Clinical Coordinating Center (CCC) at the University of Florida have established standardized systems and operational protocols to ensure data quality control.

In order to reduce chart data abstraction errors and inconsistencies and improve data quality, HCV-TARGET utilizes a specially trained Centralized Chart Data Abstraction team at the CCC as the method for chart abstraction. Participating sites provide de-identified copies of clinically available source data on enrolled participants to the CCC. This data includes ALL clinic notes, nursing/staff telephone notes, evaluations and lab results collected to monitor the HCV baseline condition, on-treatment safety and efficacy as well as long term health outcomes. The Centralized Chart Abstraction or respective country Abstraction Core team will abstract and enter the data from those provided participant de-identified medical records. Those records are maintained at the CCC or Abstraction Core to facilitate data monitoring as needed.

DCC personnel in conjunction with the CCC will closely monitor clinical center adherence to study protocol and data collection practices for complete and accurate research data. Monitoring is performed following an established Data Management and Clinical Monitoring Plan to facilitate the smooth conduct of the study. At the time of the on-site visit, DCC personnel will have access to all study and patient documents and to clinical center personnel. All patient and study documents will be kept confidential. Identifiers such as patient name and address can be viewed by the DCC or CCC to facilitate remote monitoring, but these identifiers will not be included on any datasets used for data analyses. For the purposes of Centralized Abstraction, sites will redact all protected health information (PHI) identifiers from records before transmitting to the CCC. In instances where a PHI identifier is present on a record received at the CCC, delegated CCC personnel will redact that information.

The DCC resides in the Biomedical Informatics Core of the UNC- Chapel Hill CTSA-funded TraCS Institute. The database is housed within a secure server environment of the data center on the UNC campus, and is governed by the standard University of School of Medicine information security guidelines.

The REDCap based data management system implemented for the HCV-TARGET registry is being adapted to the specified FDA recommendations, and annual internal audits will be performed to ensure compliance is achieved.

8.6.1. Timings of Assessment during follow-up

An interim analysis will be conducted in 2016 and the final analysis will be completed in 2018.

8.7. Data analysis

The eltrombopag cohort study nested within HCV-TARGET is a descriptive study conducted to provide primarily incidence of hepatic decompensation and secondarily other important outcomes such as thromboembolic events and mortality in HCV patients who are treated with direct acting anti-viral agents as part of their interferon-based regimen, a group of patients not previously studied in the randomized clinical trials. Cumulative incidence rates will be calculated for the occurrence of hepatic decompensation, thromboembolic events, or mortality, as separate events, at multiple time points during the study and at the end of the 3-year follow-up period. The 95% CIs for cumulative incidence will be calculated using the method outlined by Newcombe et al [Newcombe, 1998]. Baseline factors potentially related to each event will be identified during exploratory analyses by comparing Kaplan-Meier survival estimates for patients with vs. without the factor and testing for statistical significance using the log-rank test. Cox proportional hazards models will be constructed to evaluate the influence of these identified factors simultaneously.

Kaplan-Meier survival estimates will be calculated for the outcomes of hepatic decompensation, thromboembolic events, and all-cause mortality. Thromboembolic events will be presented as a single category as well as grouped by venous or arterial origin, and by individual event types. Confidence intervals for survival rates will be calculated using the method outlined by Simon et al [Simon, 1986]

Patient demographics and characteristics will be described at the time of initiation of eltrombopag. Virology, laboratory information, information on dose and duration of eltrombopag, early and sustained virologic response, anti-viral therapy and incidence of hepatic decompensation and thromboembolic events will be described at baseline and distinct follow-up time points. Continuous variables will be reported as mean, standard deviation, median, 25th and 75th quartiles, and range. Categorical variables will be summarized as number and proportion of subjects with observed (non-missing) data, with corresponding 95% confidence intervals (CI) by exact methods.

The number and percentage of patients who achieve early virologic response and sustained virologic response will be reported at distinct follow-up time points. The probability of attaining SVR by these time points will be presented as Kaplan-Meier estimates, along with median time to attaining SVR.

For the long term outcomes of hepatic decompensation or mortality at 3 years (as separate events), incidence rate ratios comparing eltrombopag patients who did vs. did not attain SVR will be calculated, along with 95% confidence intervals using the method outlined by Dobson et al [Dobson, 1991]. For eltrombopag patients with less than three years of follow-up, survival analyses will be used to take censoring into account. Kaplan-Meier survival graphs will be plotted and the log rank test will be used to determine statistical significance of SVR (after assuming proportionality assumptions). Factors determined to be related to hepatic decompensation (or to all-cause mortality in a separate analysis) from the earlier exploratory work will be included in a multivariate Cox proportional hazards model along with SVR to determine independence of SVR as a predictor variable.

For those patients who are lost to follow-up, or who drop out of the study, the analyses will include all data up to the point of their last data collection.

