***Data analysis**

Cumulative incidence rates and corresponding 95% confidence intervals as well as Kaplan-Meier rates and corresponding 95% confidence intervals will be calculated for the occurrence of hepatic decompensation, thromboembolic events, or mortality, as separate events, at multiple time points during and at the end of the 3-year follow-up period. Baseline factors potentially predictive of events will be identified through Kaplan-Meier survival estimates for patients with vs. without the factor and testing for statistical significance using the log-rank test. Cox proportional hazards models will be constructed to evaluate the influence of these identified factors simultaneously.

Patient demographics and characteristics will be described at the time of initiation of eltrombopag. Virology, laboratory information, information on dose and duration of eltrombopag, early and sustained virologic response, anti-viral therapy and incidence of hepatic decompensation and thromboembolic events will be described at baseline and distinct follow-up time points. Continuous variables will be reported as mean, standard deviation, median, 25th and 75th quartiles, and range. Categorical variables will be summarized as number and proportion of subjects with observed (non-missing) data, with corresponding 95% confidence intervals (CI) by exact methods.

The number and percentage of patients who achieve early virologic response and sustained virologic response will be reported at distinct follow-up time points. The probability of attaining EVR and SVR by these time points will be presented as Kaplan-Meier estimates, along with median time to attaining virologic response.

***Milestones.** An interim analysis will be conducted in 2016 and the final analysis will be completed in 2018.

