7. RESEARCH QUESTION AND OBJECTIVE(S)

The primary objective of this study is to report the incidence of hepatic decompensation in patients with chronic hepatitis C virus infection who receive eltrombopag therapy with interferon-based therapy that also includes direct acting anti-viral agents, a group not studied in the Phase III randomized clinical trials. Secondary objectives include reporting the real-world incidence of thromboembolic events and mortality and identifying risk factors for hepatic decompensation, thromboembolic events and mortality in this group of understudied patients. The study will also report the 3-year incidence of hepatic decompensation and mortality, comparing patients who achieve sustained virologic response to patients who do not achieve SVR among eltrombopag patients treated with interferon-based therapy and direct acting agents, which has not yet been studied. The study will also examine effectiveness of eltrombopag to initiate and maintain HCV therapy and achieve EVR and SVR among patients specifically using direct-acting anti-virals with interferon-based therapy.

Specific Study Aims

- Primary: Determine the incidence of hepatic decompensation among patients receiving eltrombopag with interferon-based therapy and direct acting anti-viral agents,
Secondary:
- Determine the incidence of thromboembolic events and mortality among patients receiving eltrombopag with interferon-based therapy and direct acting anti-viral agents
 - Explore factors associated with risk of hepatic decompensation and risk of thromboembolic events among patients receiving eltrombopag with interferon-based therapy and direct acting anti-viral agents
 - Determine the incidence rate ratio of hepatic decompensation and mortality at 3 years, comparing eltrombopag patients achieving sustained virologic response to eltrombopag patients who did not achieve SVR in the setting of treatment with interferon-based therapy and direct acting anti-viral agents
 - Obtain information on treatment effectiveness among patients receiving eltrombopag with interferon-based therapy and direct acting anti-virals with respect to initiating, maintaining and completing HCV therapy, and achieving EVR and SVR

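### The risk-factor screen in 8.7 and the Abstract is written only as a two-group log-rank comparison, so continuous baseline measures would have to be dichotomised before they can be tested

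*Protocol*

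**What the plan says.** Section 8.7 of the protocol places the search for risk factors among its exploratory analyses and gives one method for it: "comparing Kaplan-Meier survival estimates for patients with vs. without the factor and testing for statistical significance using the log-rank test". The Abstract, under Data analysis, gives the same method: "Baseline factors potentially predictive of events will be identified through Kaplan-Meier survival estimates for patients with vs. without the factor". Section 8.7 continues: "Cox proportional hazards models will be constructed to evaluate the influence of these identified factors simultaneously". Later in 8.7, the factors found in that exploratory work, together with SVR, form the multivariable Cox model used to judge whether SVR is an independent predictor.

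The candidate factors are listed elsewhere. Section 8.3.3 has "Demographics: Age, Sex, Race/ethnicity", followed by co-morbidities, virology, cirrhosis and concomitant medication. Section 8.4 adds "Baseline factors (HCV viral load, HCV genotype, cirrhosis determination, prior HCV treatment, medical history, co-morbid conditions, IL-28b genotypes". Section 8.7 also describes laboratory information at baseline. The corresponding secondary aim in section 7 begins "Explore factors associated with risk of hepatic decompensation and risk of thromboembolic events".

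**The concern.** Diabetes, cirrhosis, HIV coinfection or baseline ascites divide patients into those who have the factor and those who do not. An age, a viral load or a laboratory value does not. If the two-group comparison is the only route by which a factor is identified, every continuous measure has to be split before it can be tested.

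Splitting discards information, and there is little to spare: about 10 decompensation events are expected. Two things are at stake. A continuous measure that truly predicts decompensation is less likely to pass the screen. If it fails, it is also missing from the multivariable Cox model and from the model that adjusts the SVR comparison, because both are built from the factors that passed.

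**Working it through.** **Does the plan give a figure for this?** No. Section 8.5 gives half-widths for incidence and power for users against non-users (19% at 1:1 matching to 44% at 1:6). Those power values reproduce with a continuity-corrected two-proportion test (10% vs 5%, 100 users, two-sided 5%): 18.7% and 43.7%. They concern a different comparison, so the size of this problem has to be worked out separately.

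**Inputs from the protocol.**
- Projected cohort, section 8.5: "it is estimated that 105 eltrombopag patients will comprise the nested HCV-TARGET cohort study when all 5000 HCV-TARGET patients have been enrolled". This is 5000 × 0.021 = 105.
- Range of cohort size, section 8.5: "for a sample size between 50 and 150 patients".
- Decompensation rate, section 8.5: 10%, varied from 8% to 12%.
- Expected events: 105 × 0.10 = 10.5 (8.4 at 8%, 12.6 at 12%); 50 × 0.10 = 5; 150 × 0.10 = 15.

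**Assumptions not in the protocol.** A normally distributed predictor, a log-linear effect on the hazard, hazard ratio (HR) 2 per SD (also 1.5), a two-sided 5% test, complete fixed follow-up, and the position of the cut.

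**Analytic approximation.** With D events, power ≈ Φ(r·√D·ln HR − 1.96). Here r = 1 for the continuous measure and r = √(2/π) = 0.798 for a median split of a normal variable.
- Continuous, D = 10.5, HR 2: 3.240 × 0.693 = 2.246; 2.246 − 1.96 = 0.286; Φ = 61.3%.
- Median split: 2.246 × 0.798 = 1.792; 1.792 − 1.96 = −0.168; Φ = 43.3%.
- Loss: 18 points.
- HR 1.5: 25.9% against 18.1%, a loss of 8 points.

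**Simulation.** Exponential event times, score test on the continuous value against the log-rank test on the split value, 20,000 cohorts per row, 10% events:

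| Users | HR per SD | Continuous | Median cut | Upper-quartile cut | Lower-quartile cut |
|---|---|---|---|---|---|
| 105 | 2 | 59.3% | 39.4% | 47.7% | 13.3% |
| 105 | 1.5 | 25.7% | 18.0% | 22.1% | 6.3% |
| 105 | 1 | 5.0% | 5.1% | 4.6% | 4.4% |
| 50 | 2 | 32.4% | 19.6% | 26.9% | 0.7% |
| 150 | 2 | 73.2% | 51.3% | 59.0% | 26.8% |

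The HR 1 row shows that all four tests hold close to 5%, so the differences are in power and not in type I error. At 105 users and HR 2 the loss is 59.3 − 39.4 = 20 points at the median and 59.3 − 47.7 = 12 points at the upper quartile. At HR 1.5 it is 8 and 4 points; repeat runs put the range at about 3 to 8. With HR 2 and 105 users, a median cut loses about 17 points at 8% events and about 21 at 12%. For thromboembolic events at 3% (about 3 events) the loss is about 10 points, from about 21% to about 11%, so either test is weak.

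The analytic approximation treats upper and lower cuts alike. The simulation does not, because at HR 2 per SD most events come from the upper tail.

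**The case against.** The strongest objection is that this reads one sentence of a descriptive study too literally. The two-group wording fits most of the covariate list, the screen is called exploratory, and the protocol never says that age or viral load will be dichotomised. Cut-points and functional form are commonly left to an analysis plan, which is not shown here.

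Part of this stands. Many listed factors are truly categorical and lose nothing, and the absence of a cut-point is not a fault in itself. But the protocol does more than leave the detail open: it names the two-group log-rank comparison in two places as the way factors are identified and offers no other. An analysis plan that follows this inherits the loss, and one that screens continuous values departs from the protocol.

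A reader might go further and infer that the dichotomised version is carried into the Cox models and leaves residual confounding in the SVR comparison. The protocol does not support that. Section 8.7 says which factors enter those models and is silent on how they are coded; continuous coding after selection is not excluded. The established loss is at the screening step.

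A reader might also take the loss to be larger. A figure near 22 points with a median cut appears only at about 15 events (150 users), not in the projected cohort.

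Finally, the simulation makes the log-linear model exactly right, which favours the continuous test. Even that test has only about 59% power at HR 2 and 26% at HR 1.5, so many moderate predictors would be missed either way. Section 8.5 also says that the SVR comparison is not powered and is addressed in a separate study. These points limit the practical effect; they do not justify the less efficient screen.

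**Conclusion.** The concern holds for the screening step. Followed as written, 8.7 and the Abstract force continuous baseline measures into two groups before they can be identified as risk factors. In the projected cohort of 105 with 10% events, this costs about 20 points of power with a median cut and about 12 with an upper-quartile cut, under an assumed normal predictor with a log-linear HR of 2 per SD. At HR 1.5 per SD it costs about 3 to 8 points. These effect sizes, the distribution and the cuts are assumptions, because the protocol gives none.

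A predictor missed at the screen is also absent from the multivariable and SVR-adjusted Cox models. The matter is confined to an exploratory secondary analysis and leaves the primary estimate of decompensation incidence untouched.

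**What to change.** In 8.7 and the Abstract:
- Limit the log-rank comparison to categorical factors, such as sex, cirrhosis, diabetes and baseline ascites.
- Screen continuous baseline measures (age, log10 HCV viral load, laboratory values) by univariable Cox regression on the continuous scale, reporting the hazard ratio per SD or per stated unit.
- State that the same continuous form is used in the multivariable and SVR-adjusted Cox models.
- Keep Kaplan-Meier curves by group for these measures as display only.

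The cost is about two sentences in each place, with no new data and no more patients. The small downside is the assumed log-linear effect, which about 10 events can check only weakly; hazard ratios per unit are also a little less direct to read than two curves.
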